#### **10.1.7      Electrocardiogram**

A 12-lead ECG will be obtained according to the Schedule of Assessments ([Table 3](#)). Subjects must rest in the supine position for at least 10 minutes before the ECG recording is started. The ECG should be recorded during the period of rest required before blood collection and the measurements of orthostatic blood pressure, pulse rate, and respiratory rate. A qualified physician will review the ECGs and any clinically important finding will be recorded on the appropriate CRF. The investigator is responsible for providing interpretation of all ECGs. The results will include heart rate, PR interval, QRS interval, QT interval, and QTc interval, and assessment of rhythm and morphology. If necessary, (e.g., suspected QTc prolongation), a manual reading of the ECG data will be performed.

In some cases, it may be appropriate to repeat abnormal ECGs to rule out improper lead placement as contributing to the ECG abnormality. It is important that leads are placed in the same positions each time in order to achieve precise ECG recordings. If a machine-read QTc value is prolonged, as defined above, repeat measurements may not be necessary if a

qualified physician's interpretation determines that the QTc values are in the acceptable range.

#### **10.1.8      Columbia-Suicide Severity Rating Scale**

The C-SSRS is a suicidal ideation rating scale created by researchers at Columbia University ([Posner, 2011](#)). It rates an individual's degree of suicidal ideation on a scale, ranging from "wish to be dead" to "active suicidal ideation with specific plan and intent."

The scale identifies behaviors that may be indicative of an individual's intent to commit suicide. The C-SSRS is used extensively across primary care, clinical practice, surveillance, research, and institutional settings. It is available in more than 100 country-specific languages and is part of a national and international public health initiative involving the assessment of suicidal ideation and behavior.

The C-SSRS requires no mental health training to administer. An electronic patient-reported version of the C-SSRS is also available in tablet, interactive voice response, and web versions ([Mundt 2010](#); [Mundt 2013](#)).

Subjects with a history of attempted suicide within the past year or a C-SSRS score of 4 or 5 at screening will be excluded from the study. Subjects who answer "yes" to Suicidal Ideation item 4 or 5 on the C-SSRS during the study must be withdrawn from study treatment. Investigators should also withdraw subjects from treatment if, in the judgment of the investigator, the subject develops other indicators of significant risk of suicide. In the event that suicidal ideation is observed in any study subject, the investigator will manage the situation as he/she deems medically and psychiatrically appropriate.

The "lifetime" version of the C-SSRS will be used at screening, and the "since last visit" version will be used at all other visits.

Samples of the C-SSRS are provided in [Appendix A1](#).

#### **10.1.9      University of Miami Parkinson's Disease Hallucinations Questionnaire**

The UM-PDHQ was specifically developed to quantitatively and qualitatively assess hallucinations in patients with Parkinson's disease ([Papapetropoulos, 2008](#)). The UM-PDHQ is a 20-item clinician-administered questionnaire that is completed during a structured interview. Questions are divided into 2 groups: a quantitative group that consists of 6 questions (modality, frequency, duration, insight, emotional burden) and a qualitative group that consists of 14 questions. The first item is a gating question to assess the presence or absence of hallucinations.

The investigator will complete the UM-PDHQ for any subject who experiences visual hallucinations during the study. The investigator should discuss the continued participation of any subject developing visual hallucinations during the study with the study safety representative.

A copy of the UM-PDHQ is provided in [Appendix A2](#).

## 10.2 Adverse Events

### 10.2.1 Definitions

#### Adverse Event

An AE is any unfavorable or unintended sign (including an abnormal laboratory finding), symptom, or disease temporally associated with the use of a medical treatment or procedure that may or may not be considered related to the medical treatment or procedure.

Seizure should not be reported as an AE or SAE unless it is a new seizure type, the frequency of seizure increases, status epilepticus occurs, or the investigator considers the seizure to be an AE or SAE.

#### Adverse Events of Special Interest

The following are considered AESIs: increase in seizure frequency, new seizure type, and status epilepticus.

#### Laboratory Abnormality

A laboratory abnormality is any clinically significant laboratory abnormality that suggests a disease or organ toxicity and that is of a severity to require active management (i.e., changes of dose, discontinuation of drug, more frequent follow-up, medical treatment, diagnostic investigation). Laboratory abnormalities are also considered AEs.

#### Treatment-emergent Adverse Events

Treatment-emergent adverse events (TEAEs) are all AEs occurring during the treatment period or a pretreatment event that worsens in intensity during the treatment period.

#### Treatment Period

The treatment period is the period during which a subject receives study drug (i.e., first dose through Day 26).

#### Intolerable Adverse Event

An intolerable AE is one that is considered by the investigator to be related to study drug ([Section 10.2.2.3](#)) AND is either a severe or life-threatening event ([Section 10.2.2.2](#)) OR is a mild or moderate event that prompts the subject to express a desire to discontinue dosing. Dose adjustments for intolerable AEs are described in [Section 4.6](#).

#### Serious Adverse Event

An SAE is any adverse event that results in death, is life threatening, requires inpatient hospitalization or prolongation of existing hospitalization, results in persistent or significant disability/incapacity, is a congenital anomaly/birth defect observed in any offspring of the subject conceived during treatment with the study drug, or is an important medical event. See [Section 10.3](#) for more details on SAEs.

## **10.2.2 Collection and Rating of Adverse Events**

All AEs, irrespective of the relatedness to the study drug, will be captured from the time the ICF is signed through the telephone safety check on Day 33. SAEs will be reported up to 30 days after the last dose of study drug. A follow-up phone call will be made 30 days after the last dose of study drug for evaluation of any SAEs. In case of an SAE, an SAE Report Form must be completed and transmitted to the sponsor or designee within 24 hours.

Overdoses and medication errors in the presence of clinical consequences should be recorded as AEs. The clinical consequence should be reported as “[enter AE] due to overdose.” See [Section 4.7](#) for overdose management.

### **10.2.2.1 Onset Date**

The onset date is the date when the first sign(s) or symptom(s) were first noted. For example, if the AE is an abnormal laboratory test (such as “platelets low”), the onset date is the date when the sample was taken. If the subject was hospitalized for meningitis, and symptoms such as fever, headache, and nausea started the day before the hospitalization, the onset date is the day symptoms presented versus day of hospitalization.

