## 4.3 Administration

CX-8998 will be administered as:

1. Days 1 – 2: 2 mg (1 capsule) BID (4 mg/d);
2. Days 3 – 8: 4 mg (2 capsules) BID (8 mg/d);
3. Days 9 - 14: 6 mg (3 capsules) BID (12 mg/d);
4. Days 15 – 20: 8 mg (4 capsules) BID (16 mg/d);
5. Days 21 - 26: 10 mg (5 capsules) BID (20 mg/d).

Study drug should be administered with food. Subjects should be instructed to take their daily dose at approximately the same times each day. Consecutive doses should be taken no closer than 10 hours and no later than 14 hours (every 12 hours  $\pm$  2 hours). Subjects will remain under observation for at least 4 hours post-dosing prior to discharge at Visit 1.

At the Day 26 clinic visit at which 2 postdose PK blood draws,  $>2$  hours apart, are scheduled to be obtained, subjects will take the morning dose at the appropriate time. Both the time of the morning dose and the time of the PK blood draw will be recorded.

A missed dose ( $>14$  hours since the prior dose) should be skipped and should not be “doubled-up” or “made up”; the next dose should be taken 24 hours from the last administered dose. If the subject experiences emesis following the dose, that dose should not be re-taken; instead the next dose should be taken 24 hours from the last administered dose without emesis. If emesis occurs, the subject should contact the investigator or qualified designee at the study site for guidance on management of the emesis.

Treatment compliance will be assessed as described in [Section 4.5.1](#).

Subjects experiencing specified AEs will have their dose adjusted. See [Section 4.6](#) for details on dose adjustments.

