**Table 3 Schedule of Assessments**

Visit	Screening	Dosing Period										EOT	EOS	FU	
		Day	-28 to -1	1	2	3-7	8	9-13	14	15-19	20	21-25			
Visit Window			-	0		-2 d		-2 d		-2 d			±1 d	±1 d	±2 d
CX-8998 daily dose	-		4 mg		8 mg		12 mg		16 mg		20 mg				
Clinic visit	X	X										X 			
Telephone call 				X		X 		X 		X 			X 	X	
Informed consent 	X														
Demography/medical history 	X														
Eligibility criteria	X	X													
Complete physical exam	X											X			
Targeted physical exam 		X													
Neurological exam	X											X			
Vital signs 	X	X										X			
Electrocardiogram 	X	X										X			
Clinical laboratory tests 	X	X										X			
Urine (+/- serum) pregnancy test 	X											X			
Serum FSH 	X														
Drug screening 	X											X			
Pharmacogenomics sample 		X													
Blood sampling for PK 		X										X			
Video EEG + HV and PS 	X											X			
Video-EEG 	X											X			
Seizure-related Disability Assessment Scale		X										X			

Visit	Screening	Dosing Period										EOT	EOS	FU
Day	-28 to -1	1	2	3-7	8	9-13	14	15-19	20	21-25	26	33	57	
Visit Window		-	0		-2 d		-2 d		-2 d		±1 d	±1 d	±2 d	
CX-8998 daily dose	-	4 mg		8 mg		12 mg		16 mg		20 mg				
Clinic visit	X	X									X 			
Telephone call 			X		X 		X 		X 			X 	X	
Daily Seizure Diary	X	X	X	X	X	X	X	X	X	X				
C-SSRS 	X	X									X			
UM-PDHQ 		As needed												
Prior / concomitant meds	X	X			X		X		X		X			
AE review 		X			X		X		X		X	X	X 	
Study drug admin. in clinic		X 									X 			
Study drug admin. outpatient		X 	X	X	X	X	X	X	X	X	X 			
Drug compliance											X 			

AE = adverse event; C-SSRS = Columbia-Suicide Severity Rating Scale; ECG = electrocardiogram; EEG = electroencephalogram; EOS = end of study; EOT = end of treatment; FSH = follicle-stimulating hormone; FU = follow-up; HIV = human immunodeficiency virus; HV = hyperventilation, PK = pharmacokinetic;

PS = photic stimulation; UM-PDHQ – University of Miami Parkinson’s Disease Hallucinations Questionnaire.

1. Visit window ± 1 day as needed for scheduling.

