#### **7.2.8      End of Study Visit (Day 26)**

Subjects will return to the clinic for the final visit assessments detailed in [Table 3](#). This visit may take place on Day 25, 26, or 27 as needed for scheduling. Subjects will be instructed to take their dose of study drug before reporting to the clinic.

A standard multi-lead video-EEG with HV and photic stimulation (PS) will be obtained over 30 minutes and will be followed by an additional 6-hour awake video-EEG (total, 6.5 hours). During this time, safety assessments, as shown in Table 3, will be conducted, and 2 PK blood samples, separated by >2 hours, will be obtained. Subjects will undergo HV for 5 minutes (HV period 1). If no absence seizure occurs, after a 5-minute rest, subjects will undergo HV for an additional 5 minutes (HV period 2). Further details, including procedures for HV and PS will be elaborated in the EEG Charter. Adverse events that are unresolved at the visit will continue to be followed by study staff as detailed in [Section 10.2.3](#).

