## 10.4 Safety Monitoring and Risk Mitigation Plan

Measures to minimize the risks to subjects enrolled in this clinical trial have been taken with respect to the following study design elements:

- Subject safety and tolerability will be monitored in this study across multiple dimensions by tracking clinical AEs; vital signs (including orthostatic pulse and blood pressure); general and neurological physical examinations; standard clinical laboratory safety panels for complete blood counts, chemistry, coagulation, and urinalysis; standard 12-lead ECGs; the C-SSRS; and the UM-PDHQ.
- The specified inclusion/exclusion criteria have been carefully considered to avoid enrollment of subjects for whom exposure to the study drug might pose a hazard.
- This study will perform a careful dose titration in which dosing of CX-8998 will be initiated at 2 mg BID for 2 days and then increased to 4 mg BID for 6 days, to 6 mg BID for 6 days, to 8 mg BID for 6 days, and, finally, if tolerated, to the target dose of 10 mg BID for 6 days. The study is designed to allow for flexible titration. The dose should only be increased if the previous dose level is well tolerated. Should subjects experience intolerable AEs (see [Section 10.2.1](#)) at 6 mg, 8 mg, or 10 mg BID, study drug may be discontinued, or the dose may be decreased to the previous lower dose. Subjects who experience intolerable AEs at 2 mg or 4 mg BID will be discontinued from treatment.
- Dose modification and stopping rules are in place for individual subjects (see [Section 4.4](#)). Near real-time safety and tolerability monitoring for individual subjects is the primary responsibility of the principal investigators and sub-investigators.
- All SAEs meeting criteria for expedited reporting to the US FDA will be reported to the FDA and all institutional review boards (IRBs) in accordance with regulatory timelines.
- The sponsor's Study Safety Representative will monitor aggregate study level safety and tolerability after approximately 50% of the projected sample size of subjects have completed the EOS Visit. These reviews will be based on blinded, select listings and summary tables of the evolving safety and tolerability data for each arm of the study. Decision-making will depend on the specifics of the safety and tolerability data reviewed.

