5.3.2.3. Adverse Events

Adverse events will be mapped to a Medical Dictionary for Regulatory Activities (MedDRA) preferred term and system organ classification, version 21.0. If a subject experiences multiple events that map to a single preferred term, the greatest severity grade and strongest assessment of relationship to study medication, as determined by the investigator, will be assigned to the preferred term for the appropriate summaries. Adverse events that have a missing severity will be classified as having the greatest severity. Adverse events that have a missing relationship will be classified as having the strongest relationship to study medication.

A summary of TEAEs will be presented to show the number and percentage of subjects with at least one AE, SAE, AESI, related AE, or Grade 3 or higher AE.

The occurrence of TEAEs will be summarized by treatment group using system organ class, preferred term, and severity. Separate summaries of treatment-emergent SAEs, AESI, TEAEs related to study drug, and TEAEs leading to the discontinuation of study treatment, and TEAEs by CX-8998 dose administered will be generated. Adverse events will be assigned to a respective CX-8998 according to the start date of the adverse event.

All TEAEs will be listed for individual subjects. The listing will show both verbatim and preferred terms, along with the system organ class and other data gathered regarding the event. All AEs that have start dates prior to the initiation of study treatment will be excluded from the tables but will be included in the listings.

Determination of treatment emergence will be determined according to the rules outlined in Section 3.3.5.

The following are considered AEs of special interest: increase in seizure frequency, new seizure type, and status epilepticus. Otherwise; seizures are not reported as AEs or SAEs.

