14.3.1.1 Summary of Treatment-Emergent Adverse Events

14.3.1.2 Treatment-Emergent Adverse Events by System Organ Class, Preferred Term, and Greatest Severity

14.3.1.3 Treatment-Emergent Adverse Events Related to Study Drug by System Organ Class and Preferred Term

14.3.1.4 Treatment-Emergent Adverse Events by CX-8998 Dose Administered, System Organ Class, and Preferred Term

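### Table 14.3.1.4 will show a laboratory AE first found at the Day 26 draw under the last dose received, although the data cannot say at which dose it began

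*Protocol*

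**What the plan says.** **Dating.** Protocol 10.2.2.1 takes onset as the date a sign or symptom was first noted. For an abnormal laboratory test it specifies that "the onset date is the date when the sample was taken". Protocol 10.2.1 limits laboratory abnormalities to clinically significant ones that need active management, and adds: "Laboratory abnormalities are also considered AEs".

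**Sampling.** In protocol Table 3 the row "Clinical laboratory tests" is marked at Screening, Day 1 and the Day 26 clinic visit. The SAP's schedule (section 1.2, based on amendment 3, under which the data were collected) has the same three marks. Its Day 8 and Day 20 nurse home visits carry no laboratory mark.

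**Assignment.** SAP 5.3.2.3 states: "Adverse events will be assigned to a respective CX-8998 according to the start date of the adverse event". The word 'dose' appears to be missing after the drug name. The output title in SAP section 10, Table 14.3.1.4, makes the intention clear: "Treatment-Emergent Adverse Events by CX-8998 Dose Administered, System Organ Class, and Preferred Term". Neither document has a separate rule for laboratory AEs or a caveat on this table.

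**The concern.** Each rule is reasonable alone. A sample date is a sound record of when an abnormality was first detected. The difficulty arises when the SAP uses that detection date as though it identified the dose at onset.

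For a symptom, the two dates are close. For a laboratory finding with no scheduled sample from Day 2 to Day 25, they can be more than three weeks apart, and the subject may have passed through all five dose steps in between.

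Safety and tolerability is the primary objective, and Table 14.3.1.4 is the only AE table in the SAP's list that is broken down by dose. Empty lower-dose columns would look like an absence of laboratory AEs at those doses, when no scheduled sample was taken there. In a study of this size, one or two events placed this way could shape how the table reads.

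**Working it through.** The plan states no figure on this point, so there is none to reproduce. The check sets the sampling schedule against the titration calendar.

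**1. Days per step.** Protocol 10.4 describes dosing "initiated at 2 mg BID for 2 days and then increased to 4 mg BID for 6 days", then 6 days each at 6, 8 and 10 mg BID. Protocol 4.3 gives the same calendar. The steps last 2, 6, 6, 6 and 6 days at 4, 8, 12, 16 and 20 mg/d, 26 days in total. Days below the top step: 2 + 6 + 6 + 6 = 20, and 20/26 = 77%.

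**2. Scheduled samples per step.**
- Screening precedes treatment and cannot give an on-treatment onset.
- Day 1 falls in the 4 mg/d step. The documents do not say whether this laboratory sample is predose. If it is, it serves as baseline; if not, it could record an event at 4 mg/d.
- No sample is scheduled in the 8, 12 or 16 mg/d steps.
- Day 26 falls in the 20 mg/d step. On the window, protocol 7.2.8 says: "This visit may take place on Day 25, 26, or 27 as needed for scheduling". None of these days precedes Day 21, so for a subject still on 10 mg BID the window does not change the column. The share of elapsed days below the top step is 20/25 = 80%, 20/26 = 77% or 20/27 = 74%.

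**3. Share that began at a lower dose.** This applies to subjects still on 10 mg BID at the Day 26 draw. It needs an assumed onset pattern, because the documents give none. Share below the top step = 1 − (top-step weight ÷ total weight), with weight = days × (daily dose)^p. The totals are:
- p = 1: 2×4 + 6×8 + 6×12 + 6×16 + 6×20 = 344
- p = 2: 2×16 + 6×64 + 6×144 + 6×256 + 6×400 = 5216
- p = 3: 2×64 + 6×512 + 6×1728 + 6×4096 + 6×8000 = 86144

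| Assumed onset pattern | Top-step share | Began below 20 mg/d |
|---|---|---|
| Uniform over days (p = 0) | 6/26 = 0.231 | 77% |
| Proportional to dose | 120/344 = 0.349 | 65% |
| Proportional to dose squared | 2400/5216 = 0.460 | 54% |
| Proportional to dose cubed | 48000/86144 = 0.557 | 44% |
| Only at the top dose | 1 | 0% |

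Every row also assumes that an abnormality, once begun, is still present at Day 26.

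**4. Subjects not on 10 mg BID at the last draw.** Under protocol 4.6 a reduced subject is on 8, 6 or 4 mg BID. Under 6.4.1 a subject removed for an AE has the end-of-study assessments, so the sample may come earlier. Their laboratory AEs go to the dose then in force or last received. If 0% to 40% of subjects were reduced or stopped (assumed), and laboratory AEs were equally likely in all subjects, 100% to 60% of laboratory AEs from scheduled samples would fall in the 20 mg/d column.

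**5. Number of events.** If 5% to 20% of 15 subjects had a laboratory AE (assumed), the count is 0.05 × 15 = 0.75 to 0.20 × 15 = 3, or about 1 to 3 events.

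**The case against.** The strongest reply accepts the mechanics and disputes the consequence.

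- **Few events.** Only abnormalities that are clinically significant and need management qualify as AEs, in up to about 15 subjects. This stands and limits the importance of the point.
- **Laboratory safety is reported elsewhere.** SAP 5.3.2.2 gives values, changes and shift tables by visit, with no dose label, and the listings carry individual results and the dose-change log. This also stands. A careful reader could reconstruct the position from them, but nothing in Table 14.3.1.4 prompts that.
- **Dose is confounded with time for every AE in a single-arm titration.** True, and the table cannot establish a dose-response for symptoms either. The laboratory problem is additional: a symptom is at least placed at the dose being taken when it began.
- **The percentages are not bounds.** Correct. The table above runs from 77% to 0%. Transient early abnormalities would have resolved unseen, so those detected lean toward later onset and the uniform 77% is probably too high.

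A reader might infer that nearly every laboratory AE will appear at the top dose. The documents do not support that: it depends on how many subjects are reduced or stopped early, for which no rate is given, and unscheduled or repeat samples may date some events earlier. A reader might also infer that the table will misdirect dose selection. No document gives it that role: the analysis is descriptive, no formal hypothesis is tested, and exposure-safety work is reported separately.

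**Conclusion.** The point holds in a limited form. For a laboratory AE first found at the Day 26 draw, the rule in SAP 5.3.2.3 names a dose at onset that the data cannot identify. The AE appears under the last dose received, which is 20 mg/d only for subjects still on 10 mg BID. Its onset could lie anywhere between the previous sample and that draw, and 20 of the 26 scheduled dosing days are below the top step. In a fully titrated subject, the 8, 12 and 16 mg/d columns have no scheduled opportunity to record such an event.

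These statements follow from the schedule and need no assumption about onset. How many events are actually misplaced is unknown: it depends on onset timing, persistence to Day 26 and dose changes, and the count is likely to be small. AEs dated from a symptom are unaffected. The onset-date rule in protocol 10.2.2.1 is not at fault; what needs correcting is the use made of it in the SAP.

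**What to change.** In SAP 5.3.2.3, restore the missing word 'dose' and add a rule for Table 14.3.1.4:

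- AEs identified solely from a scheduled laboratory sample stay in all overall TEAE tables. In Table 14.3.1.4 they go in a separate column, *dose at onset not attributable*.
- Listing 16.2.7 shows two dates for each: the last prior sample without the abnormality or worsening, and the detecting sample. Wording it this way also covers subjects who were abnormal at baseline and then worsened.
- The flag must not rest on the date alone. Day 1 and Day 26 are clinic days, and a symptom starting on either is correctly dated and belongs under its dose.

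The minimum alternative is a footnote to Table 14.3.1.4 that identifies these events and says their onset cannot be placed at a dose step.

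The cost is one sentence in the SAP and one derived flag, using sample dates and prior results already collected. The small downside is that a few AEs no longer appear under a dose column.
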